Borderline personality disorder (BPD) is a major mental illness, which is both prevalent and disabling. BPD is present in up to 18% and 25% of individuals in inpatient and outpatient psychiatric settings, respectively (1). According to recent findings, this disorder occurs in nearly 6% of the general population (2). Patients with BPD demonstrate extensive psychopathology which spans multiple symptom domains, including affective dysregulation, anxiety, impulsivity, self-injurious behaviors, psychosis (paranoia and hallucinations), dissociation, and chronic interpersonal difficulties. Also, up to 84% of patients make some form of suicide attempt, and up to 10% complete suicide (1). While individuals with BPD may present a superficially intact social façade, they often under-achieve, feel miserable, and lead very troubled lives. Furthermore, high percentages of BPD patients suffer from comorbid psychiatric illnesses (1), such as major depression (50%), dysthymia (70%), bipolar disorder (9-11%), post-traumatic stress disorder (40%), substance use disorders (35%), and eating disorders (5-20%). BPD worsens the clinical course of co-occurring Axis I disorders and limits their treatment responsiveness. For example, Gunderson et al. (2004) found that the presence of BPD significantly reduced the rate of major depressive disorder (MDD) remissions. In this study, remissions of BPD symptoms frequently were followed by MDD remissions (3). BPD is a substantial and often unaddressed barrier to lessening the individual, family, and societal burden of other severe mental illnesses.

Substantial progress has been made in the development and empirical validation of specialized psychotherapies for BPD (1). These specific approaches address BPD based upon their respective theories of the etiology and the psychological underpinnings of the illness. Currently, pharmacotherapy plays a prominent role in BPD clinical management. In contrast to the specialized psychotherapies, available psychotropic agents were not designed for BPD and are seemingly more suited to other psychiatric populations. BPD patients are exposed to the marked costs and side effects of medications in the face of often minimal symptom amelioration. To date, no medication treats BPD as a whole (1). BPD patients need similarly specialized pharmacotherapy options, which are guided by neurobiological hypotheses and experimental findings regarding BPD's particular pathophysiologic mechanisms.

While the development of BPD is multi-determined, childhood abuse and neglect are major risk factors. In a large study of patients with BPD, 91% endorsed abuse histories, and 92% reported histories of being neglected before 18 years of age (4). Lasting neurobiological effects of this childhood adversity may contribute to BPD pathophysiology in adulthood. One such effect could be hypothalamic-pituitary-adrenal (HPA) axis dysfunction. Indeed, Rinne et al. (2002) observed a hyper-responsive HPA axis (enhanced ACTH and cortisol release following dexamethasone/corticotrophin-releasing hormone (CRH) challenge) in individuals with BPD and histories of sustained childhood abuse (5). Specifically, abused BPD patients appear to demonstrate a heightened CRH drive (6). Many BPD symptoms seemingly reflect stress sensitivity and coping deficits. Ongoing HPA axis hyper-responsiveness via elevated CRH drive may be a neurobiological substrate for the stress response impairment underlying recurrent BPD phenomenology, such as self-injury (cutting, burning, head banging, etc.), suicidality, dissociation, psychosis, extreme emotional reactivity, rage, and aggression. These are the symptoms which currently compel clinicians to turn to available medications, often with limited improvement. A drug that specifically counteracts excessive CRH drive might directly target stress-related symptoms in individuals with BPD and histories of childhood trauma.

Mifepristone is an antagonist of type II glucocorticoid (GR-II) receptors, which has shown safety, efficacy, and good tolerability in the treatment of psychotic major depression (PMD). Like BPD, HPA axis hyper-responsiveness appears to play a role in PMD pathophysiology (7). Belanoff et al. (2002) hypothesized that mifepristone causes a normalizing "resetting" of HPA axis rhythm, accounting for its efficacy in PMD (8). Mifepristone produces a marked (2- to 3- fold) compensatory increase in central cortisol levels via its antagonism of GR-II receptors. This consequent central cortisol elevation may then

be able to counteract abnormally heightened CRH activity via enhanced negative feedback mechanisms (7). Pronounced antagonism of hippocampal GR-II receptors by mifepristone may hyper-sensitize these receptors. This effect can then reestablish the negative feedback capacity of cortisol at hippocampal GR-II receptors to down-regulate HPA axis activity, as the hippocampus modulates hypothalamic function. Notably, prior research suggests that this postulated “rebalancing” of HPA axis hyperactivity (CRH overdrive) by mifepristone via central GR-II receptor blockade may persist after the discontinuation of active drug treatment. In clinical studies investigating mifepristone treatment of patients with either bipolar disorder or schizophrenia, a sustained significant decrease in peripheral cortisol level, as compared with pretreatment baseline, was observed 14 days after the discontinuation of mifepristone, which had been administered at 600 mg/day for 7 days (9). There was no significant change in cortisol level with placebo. Furthermore, previous trials of mifepristone for PMD preliminarily suggest that this agent may produce durable treatment effects on clinical symptoms which persist beyond the active drug therapy period. For example, in a large placebo-controlled trial, DeBattista et al. (2006) found that mifepristone led to significantly greater improvement of general psychiatric symptoms and positive psychotic symptoms in subjects with PMD after 7 days of active treatment which persisted to day 28 (following drug discontinuation after day 7). The significant antipsychotic benefits of mifepristone compared with placebo at day 7 appeared to persist up to day 56 (7 weeks after drug discontinuation). In this PMD trial, antidepressant benefits (at a trend level of significance) favoring mifepristone were seen at the day 56 outcome point (10). This durable (sustained) symptom benefit also was observed in an earlier open-label study of mifepristone for PMD. Significant improvements in measures of general psychiatric and depression symptomatology were reported at weeks 4 and 8 compared with pretreatment baseline levels following a circumscribed 6-day period of mifepristone administration (11).

In sum, elevated CRH activity appears to be present in BPD (6), suggesting that mifepristone may be a more targeted pharmacotherapy approach for stress-related BPD symptoms involving HPA axis dysfunction. Mifepristone may therapeutically dampen CRH overdrive in abused BPD patients. In a recent study, rats exposed to a preclinical model of developmental trauma, namely early maternal separation (MS), manifested heightened HPA responsiveness to a stress paradigm and associated cognitive impairment on laboratory measures. This cognitive impairment was ameliorated by mifepristone administration in the rats exposed to early MS (12).

2.0 Rationale

This is a proof of principle study of mifepristone in the treatment of individuals with BPD and histories of childhood abuse, which aims to translate neurobiological research concerning HPA axis abnormalities in BPD into a novel clinical intervention for patients. This project will also explore an innovative approach to the structure of pharmacotherapy for BPD. Specifically, we will employ the circumscribed (finite) drug administration period used in prior studies of mifepristone in neuropsychiatric illness, which differs from the current clinical practice of indefinite daily usage of medications. We hypothesize that mifepristone will beneficially impact stress response neurobiology and consequently ameliorate associated BPD symptoms.

3.0 Specific Aims

Specific aim 1: to evaluate whether mifepristone will produce rapid symptom reduction after seven days of active treatment, as measured by Borderline Personality Disorder Severity Index (BPDSI) total score. Further, to evaluate whether seven days of mifepristone treatment will result in a durable improvement in symptoms persisting after active treatment discontinuation, as measured by Borderline Personality

Disorder Severity Index (BPDSI) total score.

Specific aim 2: to evaluate safety and tolerability of mifepristone

Specific aim 3: to assess cortisol levels as a potential biomarker of HPA-axis engagement.

Exploratory Aims: to assess clinical and demographic moderators of response to mifepristone, including childhood abuse characteristics (e.g., type of abuse, age of onset, duration) and comorbid psychiatric illnesses.

Outcome Measures: The primary outcome measures will be the Borderline Personality Disorder Severity Index (BPDSI) total score. With this measure, we will be able to investigate specifically the effect of mifepristone on BPD's entire psychopathologic spectrum. For inclusion, all subjects must demonstrate a minimum severity of a total score ≥ 3 on the CGI-S. Secondary outcomes will include the BPDSI symptom domain subscales, the Brief Psychiatric Rating Scale (BPRS), the self-report Borderline Checklist, the Symptom Checklist-90-Revised (SCL-90-R), improvement in metacognitive capacity, and the Clinical Global Impressions-Severity (CGI-S) and Clinical Global Impressions-Improvement (CGI-I) measures. Clinical assessments will be performed by trained raters, who will be blind to subjects' treatment condition.

4.0 Study Design

This is a single site safety and proof of concept study conducted at the Indiana University Psychotic Disorders Program. Twenty four subjects with borderline personality disorder will be randomized 1:1 to double-blind treatment with oral mifepristone or matched placebo for duration of seven days, with a follow up period.

5.0 Study Population (Inclusion/Exclusion Criteria)

Inclusion Criteria:

1. 18-64 years of age at study entry
2. Female or Male
3. DSM-IV-TR diagnosis of borderline personality disorder (confirmed by SCID II) with history of abuse prior to the age of 18.
4. Able to provide informed consent
5. Inpatient or outpatient
6. Clinical stability as defined by:
 - a. Subjects must not have experienced an exacerbation of their illness within 4 weeks prior to randomization, leading to an intensification of psychiatric care in the opinion of the principal investigator. Examples of intensification of care include, but are not limited to: inpatient hospitalization, day/partial hospitalization, outpatient crisis management, or psychiatric treatment in an emergency room AND
 - b. Psychotropic treatment stability for at least 2 weeks prior to randomization (no change in dosing or addition of any new psychotropic medication)
7. Female subjects of childbearing potential must test negative for pregnancy at screening visit and agree to use the double-barrier method, as defined by 2 physical barriers such as a condom, diaphragm, or cervical occlusive cap, coupled with an additional barrier such as spermicidal foam, gel, film, cream or suppository for the duration of the study. Subjects having undergone a

hysterectomy or bilateral oophorectomy or other form of female sterilization or patients having been medically confirmed to be post-menopausal, would not require any other method of contraception.

8. Minimum severity of a total score ≥ 3 on the CGI -S
9. Must agree not to consume tonic water and grapefruit or grapefruit product for 3 days prior to beginning medication and until the final study visit

Exclusion Criteria:

1. DSM-IV TR diagnosis of (confirmed by SCID) schizophrenia or a related psychotic disorder, bipolar I disorder, or dementia
2. Subjects who are considered prisoners per the Indiana University Standard Operating Procedures for Research Involving Human Subjects.
3. Subjects with current acute, serious, or unstable medical conditions, including, but not limited to: inadequately controlled diabetes, asthma, COPD, severe hypertriglyceridemia, recent cerebrovascular accidents, acute systemic infection or immunologic disease, unstable cardiovascular disorders, malnutrition, renal gastroenterologic, respiratory, endocrinologic (particularly illnesses related to the HPA-axis, e.g., Cushing's Syndrome), neurologic, hematologic, or infectious diseases
4. Clinically significant electrocardiogram (ECG) abnormality prior to randomization including: subjects with a corrected QT interval (Bazett's; QTcB) > 450 msec (male) or >470 msec (female) prior to randomization (based on the cardiologist overread). Repeat ECGs will be conducted at the discretion of the principal investigator or medical designee
5. Use of any exclusionary medication listed in Attachment 2: Concomitant Medication.
6. Pregnant or lactating women or women who plan to become pregnant or will be lactating within one month after cessation of study medication
7. Known IQ <70 based on medical history
8. Currently using an intrauterine device (IUD)
9. History of treatment with mifepristone or any mifepristone-containing medication at any time
10. Known history of (1) Hepatitis C virus antibody, (2) Hepatitis B surface antigen (HBsAg) with or without positive Hepatitis B core total antibody, or (3) HIV 1 or 2 antibodies
11. Subjects with moderate to severe renal impairment as defined by creatinine clearance (CrCl) < 60 ml/min (measured by the Cockcroft-Gault equation) at screening
12. Subjects with hepatic impairment as defined by liver transaminases or total bilirubin $> 3 \times$ upper limit of normal (ULN)
13. Subjects considered a high risk for suicidal acts, as determined by the principal investigator.
14. Subjects who have participated in a clinical trial with any pharmacological treatment intervention for which they received study-related medication in the 4 weeks prior to screening OR Subjects currently receiving treatment (within 1 dosing interval plus 4 weeks) with an investigational depot formulation of an antipsychotic medication
15. Subjects who demonstrate overtly aggressive behavior or who are deemed to pose a homicidal risk in the principal investigator's opinion
16. Psychosocial treatment changes 14 days prior to randomization
17. History of unexplained vaginal bleeding, endometrial hyperplasia with atypia, or endometrial carcinoma

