11.0 Criteria for Rescreening, Repeat Assessments, and Discontinuation

Repeat Assessments

Screening assessments can be repeated within the screening window under the same screening number with the exception of eligibility criteria related rating scales/questionnaires. Subject diagnosis confirmation will not be repeated.

Rescreening

Subjects who screen fail may be rescreened one time, under a new screening number. If a subject is rescreened, all screening assessments (with the exception of the diagnosis confirmation) must be repeated and the stability criteria timelines must be met.

Discontinuation

Subjects will be discontinued from the active treatment phase under the following circumstances:

1. Any psychosocial treatment changes
2. Suicide attempt
3. Missing 2 or more doses of study medication
4. Becoming pregnant
5. Developing a serious infectious disease
6. Have a change in stability criteria indicated in inclusion criteria #6
7. Subjects who require treatment with any excluded concomitant medications (See Attachment 2)

If subjects discontinue from the study, discontinuation assessments will be at the discretion of the

principal investigator.

A subject may withdraw from the study medication at any time at her own request, or may be withdrawn at any time at the discretion of the principal investigator for safety, behavioral, or administrative reasons.

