12.0 Study Medication

Mifeprex tablets each contain 200 mg of mifepristone, a synthetic steroid with antiprogestational effects. The tablets are light yellow in color, cylindrical and biconvex, and are intended for oral administration only. The tablets include the inactive ingredients colloidal silica anhydrous, corn starch, povidone, microcrystalline cellulose, and magnesium stearate. Placebo tablets will look like mifepristone tablets, with matching shape, taste, and color. Mifepristone and matching placebo will be obtained from the manufacturer, Danco Laboratories in New York, NY. Study medication will be stored according to the details on the product label.

Dosing

The dosing used in this study is 600 mg by mouth once daily (see package insert for more information).

Compliance

Compliance will be assessed at each visit by direct questioning and medication count of unused medication and packaging to be returned at each visit. Adequate study medication dispensing records will be obtained.

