14.0 Adverse Events/Risks

For the purposes of collecting and evaluating all information found during this clinical study, an **adverse event** is any undesirable or unexpected experience that occurs after informed consent has been obtained without regard to the possibility of a causal relationship, and without regard to treatment group assignment. All adverse events will be documented and all serious adverse events will be reported following local Institutional Review Board (IRB) requirements.

For non-serious adverse events, research staff will question each subject and will document the occurrence and nature of presenting condition(s). Pre-existing condition(s) and any change in the pre-existing condition(s) will be documented and/or the occurrence and nature of any adverse event. Adverse events (AEs), especially those for which the relationship to study medication is not “unrelated,” will be followed up until they have returned to baseline status or stabilized at the discretion of the principal investigator. If after the follow-up period, return to baseline or stabilization cannot be established an explanation will be recorded in the source documentation.

The most common adverse events include:

- Nausea
- Vomiting

- Decreased appetite
- Diarrhea
- Fatigue
- Headache
- Dizziness
- Arthralgia
- Back pain
- High blood pressure

Females only:

- Endometrial hypertrophy
- Uterine cramping
- Vaginal bleeding

A **serious adverse event** is any adverse drug experience occurring at any dose that: results in death, is life threatening, results in inpatient hospitalization or prolongation of existing hospitalization, results in a persistent or significant disability/incapacity, or results in congenital anomaly/birth defect.

The following were considered serious adverse events in people with Cushing's syndrome and medical termination of pregnancy:

- Adrenal insufficiency
- Hypokalemia
- QT interval prolongation

It's not clear how frequently these serious adverse reactions may occur in an individual with BPD who does not have Cushing's syndrome and is not pregnant. This is because the vast majority of available safety data from clinical trials is for individuals with Cushing's syndrome or for women who used this medication for the termination of pregnancy and there is very little data available for people with neither condition.

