21. Guy W. ECDEU assessment manual for psychopharmacology. Washington, DC: US Department of Health, Education, and Welfare;338:534-537. 1976.
22. Lobbestael, Arntz, Harkema-Schouten, & Bernstein (2009). Development and psychometric evaluation of a new assessment method for childhood maltreatment experiences: The Interview for Traumatic Events in Childhood (ITEC). *Child Abuse & Neglect*, 33, 505–1517.
24. Mifeprex [package insert]. Danco Laboratories, New York, NY, 2009..
25. Korlym [package insert]. Corcept Therapeutics Inc., Menlo Park, CA, 2000.

ATTACHMENT 1
Study Procedures Table

Visit	1	2	3	4	5	6
Day		0	4	7	14	28
Visit Window (days since last visit)		14-30	4	3	7	14
Informed Consent	X					
SCID I & II	X					
Medical History	X					
Demographics	X					
Physical Exam	X					
Vitals	X	X	X	X	X	X
Verification of Preg Prevention	X	X	X	X	X	X
ECG ^a	X	X	X	X	X ^b	X ^b
CGI-S/I	X ^c	X ^c		X	X	X
BPRS		X		X	X	X
BPDSI (90-day)	X					
BPDSI (7-day)		X		X	X	X
BPD Checklist		X		X	X	X
ITEC ^d	X					
SCL-90-R		X		X	X	X
IPII		X				X
CBC	X					
CMP	X	X		X	X	X
Serum Preg test (beta HCG)	X					
Blood Cortisol Level		X		X ^e	X ^e	X ^e
Biobank Blood Sample		X				X
Pharmacokinetics ^f				X		
Urine Pregnancy Test	X	X	X	X	X	X
Adverse Events			X	X	X	X
Concomitant Medication		X	X	X	X	X
Medication Dispensation		X				
Medication Accountability			X ^g	X		

a Triplicate tracings to be collected at least 1 minute apart

b Subsequent ECG tracings will be collected at V5 and V6 at the discretion of the principal investigator

c CGI-I will not be completed at Visits 1 or 2 as there is no "improvement" score at baseline.

d Clinician may use abbreviated version of form, at principal investigator's discretion

e Subsequent blood collection to occur at the exact time of day as the baseline value (+/- 30 minutes)

f Pharmacokinetic analysis will be completed based off of time of study drug from previous day.

g Study medication will be reviewed during this visit for compliance purposes. Study medication will not be returned or dispensed at this visit

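### Required contraception ends at the Day 28 visit, about 8 to 9 days before the end of the post-drug month that exclusion 6 treats as relevant to pregnancy (minor)

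*Combined protocol and SAP*

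**What the plan says.** **Entry screen.** Section 5.0, exclusion 6, excludes "Pregnant or lactating women or women who plan to become pregnant or will be lactating within one month after cessation of study medication". It is applied at entry and its period runs from the end of dosing.

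**Contraception rule.** Section 5.0, inclusion 7, requires a negative pregnancy test at screening and double-barrier contraception, ending with "an additional barrier such as spermicidal foam, gel, film, cream or suppository for the duration of the study". It gives no extension counted from the last dose or the last visit.

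**Checks.** In Attachment 1 the row "Verification of Preg Prevention" and the urine pregnancy test are marked at all six visits. The last is Visit 6, Day 28.

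**Treatment.** Section 4.0 says subjects are "randomized 1:1 to double-blind treatment with oral mifepristone or matched placebo for duration of seven days, with a follow up period". Section 12.0 gives the dose once daily.

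**Stopping early.** Section 11.0 separates two events. For the drug: "Subjects will be discontinued from the active treatment phase under the following circumstances", followed by a list that includes becoming pregnant. For the study: "If subjects discontinue from the study, discontinuation assessments will be at the discretion of the" principal investigator. Neither sentence mentions contraception.

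**The concern.** Exclusion 6 tests what a woman plans when she enters. It cannot prevent an unplanned pregnancy; only inclusion 7 addresses that. By naming the month after the drug stops, the plan treats that month as one in which pregnancy should be avoided. The contraception rule is tied to the study calendar instead, and the calendar ends before the month does.

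Section 12.0 describes the drug as "a synthetic steroid with antiprogestational effects", and Section 14.0 says that safety data are sparse for people who have neither Cushing's syndrome nor a pregnancy being terminated. Some caution after dosing is therefore reasonable. What is at stake is the consistency of a participant-safety precaution. The effect size, its confidence interval and the sample size do not depend on it.

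**Working it through.** This is calendar arithmetic.

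**Inputs**
- Visit intervals after Visit 2 (Attachment 1): 4, 3, 7 and 14 days.
- Treatment: seven days, once daily (Sections 4.0 and 12.0).
- Post-drug period: one month (exclusion 6). Its length in days is not defined, so 28 to 31 days are used.
- First-dose day: not stated. Day 0 and Day 1 are both carried as assumptions.
- End of the study: taken as Visit 6, the last scheduled contact.

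**Plan's own figure.** 4 + 3 + 7 + 14 = 28, which reproduces the Day 28 shown for Visit 6.

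**Last dose, L.** L = first-dose day + 7 − 1. A first dose on Day 0 gives L = 6; a first dose on Day 1 gives L = 7. Day 6 is the better supported: Attachment 1 dispenses drug at Day 0, accounts for it at Day 7, and times the Day 7 drug-level sample from the previous day's dose. These entries do not rule out Day 7.

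**Days covered after the last dose.** 28 − L = 22 (L = 6) or 21 (L = 7).

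**Days not covered.** Gap = L + m − 28, where m is the month length.

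| Month length m | Gap, L = 6 | Gap, L = 7 |
|---|---|---|
| 28 | 6 | 7 |
| 29 | 7 | 8 |
| 30 | 8 | 9 |
| 31 | 9 | 10 |

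With a 30-day month, 8/30 = 27% or 9/30 = 30% of the month is uncovered. The extremes are 6/28 = 21% and 10/31 = 32%.

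**Drug stopped early, follow-up continued.** The rule still runs to Day 28 and L is smaller, so the gap shrinks by one day for each day earlier that dosing stops. With m = 30, a last dose on Day 3 gives 3 + 30 − 28 = 5 days, and on Day 4 gives 6 days.

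**Study left early.** The text does not say whether the contraception requirement continues, so no gap can be calculated.

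**The case against.** The strongest reply is that the two periods need not be equal. Exclusion 6 governs intent at entry, inclusion 7 governs conduct during participation, and nothing in the plan links them. Other precautions follow their own clocks: inclusion 9 ends the grapefruit and tonic water restriction at the final visit, and note e of Attachment 2 restricts short-acting beta agonists for one week after the drug stops. Women planning pregnancy in the month are already screened out, and completers have three weeks of required double-barrier contraception after a seven-day course. The documents give no half-life or washout period by which three weeks could be called too short.

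Most of this stands. A reader might infer that the criteria contradict each other. They do not, because both can be met in full by the same woman. A reader might also infer that women are exposed to harm after Day 28; the documents contain no risk data for those days. Nor is a pregnancy left without any route for reporting. Section 14.0 defines an adverse event as "any undesirable or unexpected experience that occurs after informed consent has been obtained" and lists congenital anomaly or birth defect among the serious outcomes, so a reported pregnancy could be handled there.

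What survives is narrower. An intent screen does not cover unplanned pregnancy, and no available text requires contraception in the last days of the month that the plan itself names.

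**Conclusion.** The point holds as a minor participant-safety mismatch. For completers, required contraception lasts 21 to 22 days after the last dose, and about 8 to 9 days of the month in exclusion 6 follow without it (6 to 10 over all the cases considered). On the better supported Day 6 last dose, the figure is 8 days for a 30-day month.

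This rests on three assumptions: the study ends for a participant at Visit 6, dosing starts on Day 0 or Day 1, and a month is 28 to 31 days. The consent pages were not available and may carry a longer instruction. If they do, the protocol criterion would still be clearer if it matched.

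It is tempting to add that women who leave the study early have a much longer gap. The documents do not support a length, because they are silent on whether the requirement continues. No estimate, error rate or sample size consideration changes.

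**What to change.** In inclusion 7, keep the present end of the contraception sentence and add: *and until one month after cessation of study medication, whichever is later, including subjects who discontinue early*.

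Using exclusion 6's own period makes the two criteria agree however a month is counted; a fixed 30 days would leave one day open in a 31-day month. The clause also settles what applies to women who stop the drug or leave the study early. Exclusion 6 and Attachment 1 can stay as they are.

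The cost is about 6 to 10 more days of contraception for each completer of childbearing potential. Because treatment is blinded, this applies in both arms. No visit, test or blood draw is added. The extra days would rest on the participant's agreement, since the last scheduled check remains Visit 6. A telephone contact at the end of the month could confirm adherence, but aligning the rule does not require it.
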